8.2. Definition of a SAE

A serious adverse event (experience) or reaction is any untoward medical occurrence that, at any dose:

a) Results in death

NOTE: Death is an outcome of an AE, and not an AE in itself. Event which led to death should be recorded with fatal outcome.

b) Is life-threatening

NOTE: The term 'life-threatening' in the definition of 'serious' refers to an event in which the patient was at risk of death at the time of the event. It does not refer to an event, which hypothetically might have caused death, if it were more severe.

c) Requires hospitalization or prolongation of existing hospitalization

NOTE: In general, hospitalization means that the patient has been detained (usually involving at least an overnight stay) at the hospital or emergency ward for observation and/or treatment that would not have been appropriate in the physician's office or out-patient setting. Complications that occur during hospitalization are AEs. If a complication prolongs hospitalization or fulfills any other serious criteria, the event is serious. When in doubt as to whether "hospitalization" occurred, or was necessary, the AE should be considered serious.

Hospitalization for elective treatment of a pre-existing condition that did not worsen after informed consent was given is not considered an AE.

d) Results in persistent or significant disability/incapacity,

NOTE: The term disability means a substantial disruption of a person's ability to conduct normal life functions. This definition is not intended to include experiences of relatively minor medical significance such as

uncomplicated headache, nausea, vomiting, diarrhea, influenza, and accidental trauma (e.g. sprained ankle) which may interfere or prevent everyday life functions but do not constitute a substantial disruption.

- e) Is a congenital anomaly/birth defect
- f) Is another medically important condition: This refers to an AE that may not be immediately lifethreatening or results in death or hospitalization but may jeopardize the patient or may require intervention to prevent one of the outcomes listed above. Based on medical and scientific judgment this should usually be considered serious.

If there is any doubt about whether or not an AE is serious, the investigator should contact the sponsor.

8.2.1. Events and/or Outcomes Not Qualifying as SAEs

Any hospitalization, or prolongation of hospitalization due to the circumstances listed below, will not be reported as SAE:

- planned medical/surgical procedure;
- planned medical/surgical admission (planned prior to entry into study, appropriate documentation required), for the disease under study;
- Administrative or social reasons (e.g. lack of housing, economic inadequacy, care-giver respite, family circumstances).

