2.1. Primary Objective

The primary objective of the study is to evaluate the safety of ABX464 versus placebo when administered on top of darunavir/ritonavir or darunavir/cobicistat.

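### The first exemption in section 8.2.1 lacks the limit that section 8.2(c) sets, so an adverse event serious only because of a scheduled admission can be kept out of SAE reporting

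*Protocol*

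**What the plan says.** Two neighbouring sections of the protocol decide when a hospital stay makes an event serious.

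Section 8.2 defines an SAE. Criterion (c) covers an untoward occurrence that "Requires hospitalization or prolongation of existing hospitalization". Its note carries one exclusion: "Hospitalization for elective treatment of a pre-existing condition that did not worsen after informed consent was given is not considered an AE". Criterion (f) adds other medically important conditions, of which the protocol says: "Based on medical and scientific judgment this should usually be considered serious".

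Section 8.2.1 then lists exemptions, introduced by: "Any hospitalization, or prolongation of hospitalization due to the circumstances listed below, will not be reported as SAE". Three circumstances follow:

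- The first is, in full, "planned medical/surgical procedure".
- The second is "planned medical/surgical admission (planned prior to entry into study, appropriate documentation required), for the disease under study".
- The third concerns administrative or social reasons and is not at issue.

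Section 2.1 states what the trial is for: "The primary objective of the study is to evaluate the safety of ABX464 versus placebo".

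**The concern.** The first exemption says nothing about when the procedure was planned, for which condition, or with what documentation. The second does, through the words "planned prior to entry into study, appropriate documentation required", but these sit inside the second item and do not govern the first. Section 8.2(c) also has a limit, tied to consent and to no worsening.

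A site could therefore apply 8.2.1 in good faith and file no SAE form for an event that 8.2(c) calls serious. Section 8.2.1 is the more specific instruction and is worded as mandatory. Whether the event counted as an SAE would then depend on whether the admission was booked or was an emergency, which says nothing about the event itself.

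At stake are the SAE line and the serious treatment-emergent event table in section 9.3, and the 24-hour SAE reporting in sections 8.4 and 8.6. Seriousness is also one of the three conditions for the safety reports in section 8.7.

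**Working it through.** No figure in the protocol bears on this, so there is nothing to reproduce. The check is to run the possible cases through both rules, reading the first exemption literally.

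| Case | Under 8.2(c) | First exemption of 8.2.1, read literally | Result |
|---|---|---|---|
| A. Elective procedure booked before consent, condition unchanged | Not an AE | Not reported as SAE | Agree |
| B. Pre-existing condition worsens after consent, scheduled admission needed | Serious | Not reported as SAE | Conflict |
| C. New event after consent, emergency admission | Serious | Not exempt | Agree |
| D. New event after consent, scheduled admission | Serious | Not reported as SAE | Conflict |
| E. As D, but another criterion of 8.2 is also met | Serious, also by that criterion | Exempts only the hospitalization | Still an SAE by the other criterion |
| F. Complication prolongs a hospital stay | Serious | Not a planned procedure, so not exempt | Agree |

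C and D differ only in how the admission was arranged. The conflict is confined to B and D, and within them to events with no other seriousness criterion.

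Two further comparisons bear on the wording:

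1. Read literally, the first exemption largely empties the second. A planned procedure for HIV infection would be exempt under the first without meeting the conditions of the second.
2. Section 8.3.2 requires an elective termination of pregnancy for medical reasons to be recorded as an SAE. That is a planned procedure, so the protocol does not treat every planned procedure as exempt. The explicit rule settles only that one case.

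Tracing an event of type B or D through the sections that would use it:

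| Use | Depends on | Event kept? |
|---|---|---|
| AE record and grading (8.4, 8.5) | Being an AE | Yes |
| Tables of grade 3 or higher events and of events leading to discontinuation (9.3) | Grade; action taken | Yes, if it qualifies |
| DLT and enrolment rules (3.1.2) | Grade and relatedness | Yes, unaffected |
| SAE line and serious treatment-emergent events (9.3) | SAE status | No |
| 24-hour SAE reporting (8.4, 8.6) | SAE status | No |

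**Size.** The protocol states no expected rate of SAEs or of hospital admissions, so no undercount can be derived. The time available is short. AEs are collected from consent to 4 weeks after the investigational product. With 2 to 4 weeks of screening (3.2) and 4 weeks of treatment, a completing patient contributes 2 + 4 + 4 = 10 to 4 + 4 + 4 = 12 weeks. Within that time an event must arise or worsen, an inpatient procedure must be scheduled for it, and no other criterion may apply.

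**The case against.** The best case for the protocol is that the two sections can be read together. Section 8.2.1 exempts a hospitalization due to a listed circumstance; it does not say that an adverse event stops being serious. An admission made necessary by a new event can be called due to that event and not to the procedure. The first exemption would then cover only elective admissions with no untoward event behind them, which is probably what the sponsor meant. Section 8.2 also has safeguards: criterion (f) would catch many events that need an inpatient procedure, doubt about whether hospitalization was necessary is resolved towards serious, and doubt about seriousness goes to the sponsor.

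Much of this stands, and it keeps the point small. It does not remove it. The benign reading has to be supplied by the reader, because the limit is written into the second item and into 8.2(c) but not into the first. The safeguards help an investigator who is in doubt, and a literal reader of the first exemption would not be. Criterion (f) rests on judgement and need not cover every scheduled admission.

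A reader might infer more than the text supports:

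- **That safety signals disappear.** They do not. The event stays in the AE data with its grade, and the DLT and stopping rules do not use SAE status.
- **That SAE status is the sole trigger for 24-hour notification.** Section 8.3.2 sets a 24-hour rule for pregnancy, which is not itself an AE or SAE. The loss concerns SAE reporting under 8.4 and 8.6.
- **That a confidence limit for the SAE rate in an arm of 21 measures the defect.** Such a limit describes any arm of that size and says nothing about how often this exemption misclassifies an event.

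**Conclusion.** The contradiction is real and its reach is narrow. Read literally, the first exemption of 8.2.1 withholds SAE status from an adverse event that began or worsened after consent and whose only seriousness criterion is a scheduled admission, while 8.2(c) makes the same event serious. The loss falls on the SAE tabulation and on 24-hour SAE reporting.

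This rests on one assumption: that at least some sites would apply 8.2.1 as written instead of resolving the conflict in favour of 8.2(c). The frequency cannot be derived from the protocol and is probably low. It is still worth correcting, because safety is the primary objective and the protocol already contains the right limit one section earlier.

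**What to change.** Reconcile the two sections on the standard of 8.2(c):

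- Limit the first exemption in 8.2.1 to procedures planned before informed consent for a condition that has not worsened since consent.
- State that an admission scheduled because of an event that began or worsened after consent is reported as an SAE.
- Carry the same wording into the SAE completion guidance for sites.

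A booked admission with no untoward event behind it is not an AE under 8.1, so the narrower wording does not draw it in.

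The cost is a sentence or two in the protocol, a slightly higher SAE count and a few more SAE forms.

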8.3. Events or Outcomes Qualifying as AEs or SAEs

8.3.1. Clinical laboratory parameters

Abnormal laboratory findings (e.g., clinical chemistry, hematology) or other abnormal assessments (e.g. vital signs) that are judged by the investigator as **clinically significant** will be recorded as AEs or SAEs if they meet the definitions of sections 8.1 and 8.2 respectively. Clinically significant abnormal laboratory findings or other abnormal assessments that are detected during the study or are present at informed consent and significantly worsen during the study will be reported as AEs or SAEs. Clinically significant abnormal laboratory findings or other abnormal assessments that are associated with the disease being studied, and are present at the start of the study but do not worsen, will **not** be reported as AEs or SAEs. However, if these findings or assessments are judged by the investigator to be more severe than expected considering the patient's condition, then they may be reported as AEs or SAEs.

8.3.2. Pregnancy report

Patients who become pregnant at any time will be immediately withdrawn from participation in the study. All appropriate withdrawal assessments may be performed at the discretion of the investigator.

The investigator will collect pregnancy information on any woman patient or partner of a male patient, who becomes pregnant and their partner while participating in this study. The investigator will record pregnancy information and submit it to ABIVAX or its designee within 24 hours after knowledge of a patient's or partner's pregnancy. The patient or partner will also be followed to determine the outcome of the pregnancy, be it full-term or prematurely terminated. Information on the status of the mother and child will be forwarded to ABIVAX or its designee. Follow-up will normally end 6 to 8 weeks following the estimated delivery date.

While pregnancy itself is not considered to be an AE or SAE, any pregnancy complication or elective termination of a pregnancy for medical reasons will be recorded as an SAE. A spontaneous abortion is always considered to be an SAE and will be reported as such.

The time period for collecting pregnancy information is identical to the time period for collecting AEs, as stated in Section 8.4, Time Period, Frequency, and Method of Detecting AEs and SAEs. Pregnancy information is collected from the signing of informed consent to 4 weeks after the last dose.

8.4. Time Period, and Frequency of Detecting AEs and SAEs

Clinical Study Protocol

All AEs and SAEs occurring from the time a patient consents to participate in the study until 4 weeks after he or she has completed or discontinued the investigational product must be recorded in the patient's eCRF. Importantly, SAEs will have to be reported, either by email or by Fax, to SIMBEC- ORION within 24 hours of awareness of an SAE.

SIMBEC ORION

[contact]

[contact]

Legislative guidance requires also reporting any **related** SAEs to be reported after the patient finished the study if the investigator becomes aware of them.

8.5. Recording AEs and SAEs

Severity of AEs will be assessed according to "Division of AIDS table for grading the severity of adult and pediatric adverse events", version 2.0 of November 2014.

Patients will be asked to report all AEs as part of the procedures performed at each study visit. The site personnel will document all AEs in the patient's medical record. All AEs subsequently must be recorded in the appropriate eCRF sections.

The following points must be recorded for each event:

- A description of the event in medical terms, not as reported by the patient;
- Date of onset (start date);
- Date of resolution (stop date);
- The time of onset with respect to administering the investigational product;
- The severity of the sign/symptom or clinically significant abnormal laboratory value according to CTC AE Classification;
- The causal relationship between the investigational product and the occurrence of each AE. This
 will be assessed by each investigator using clinical judgment. Alternative causes, such as natural
 history of the underlying diseases, concomitant medications, other risk factors and the temporal
 relationship of the event to the investigational product will have to be considered. The causality of
 all AEs should be assessed by the investigator with the following question: Is there a reasonable
 possibility that the AE may have been caused by the investigational product? And answered "NO"
 (if not related) and "YES" (if related);
- Action taken regarding the investigational product:
 - o No action;
 - o Temporary discontinuation;
 - o Permanent discontinuation;
 - o Patient's outcome:
 - Recovered without sequelae / resolved without sequelae;
 - Recovered with sequelae / resolved with sequelae;
 - o Recovering/Resolving;
 - o On-going;
 - Fatal (for SAEs only).

If in any one patient, the same AE occurs on several occasions, the AE in question must be documented and assessed anew each time.

8.6. Reporting of SAEs to ABIVAX or its designee

Throughout the study, the reporting of SAEs to the Sponsor or its designee will be done through the SAE forms.

Clinical Study Protocol

It is the investigator's responsibility to ensure that the SAE report is submitted to SIMBEC- ORION within 24 hours after knowledge of the event(s). The SAE forms or paper report forms should be completed as thoroughly as possible, with all the available details of the event and signed by the investigator or designee. An assessment of causality should always be provided at the time of the initial report. If the investigator or designee does not have all information regarding the SAE, he/she should not wait to receive additional information before completing the form and notifying SIMBEC- ORION.

Additional or follow-up information relating to the initial SAE report, will be requested, if necessary. Again, this information is to be completed and submitted through the SAE forms within 24 hours of receipt of the information.

In the rare occasion when the facsimile equipment does not work and in the absence of, the investigator should notify SIMBEC- ORION by telephone within the given timeframe, and send a copy of the SAE report form by email.

8.7. Reporting of SAEs to Regulatory Authorities

ABIVAX has a legal responsibility to notify, as appropriate, both the local regulatory authorities and other regulatory agencies about the safety of the investigational product. It is therefore important that the investigator notifies promptly ABIVAX or designee of any SAEs, in order for legal obligations and ethical responsibilities towards other patients to be met.

In addition, the investigator or designee, will comply with the local regulatory requirements (when applicable) in reporting of SAEs to the ethics committee and, if required, to the relevant government authority.

Safety reports on adverse events that are serious AND unexpected AND associated with the investigational product are prepared according to ABIVAX's policy and applicable regulations and are forwarded to the investigators. These reports are filed with the investigator brochure or other appropriate study documentation. It is the Sponsor or its designee and/or investigator's responsibility to notify the IRB or IEC of these reports, if applicable according to local requirements.

9. DATA ANALYSIS AND STATISTICAL CONSIDERATIONS

A summary of the principal features of the statistical analysis of the data will be described here, in the statistical section of the protocol. A more technical and detailed elaboration of the principal features stated in the protocol will be given in the first version of the statistical analysis plan (SAP).

Any amendments to the SAP will be clearly documented and signed prior to the final database lock including justifications and details of their potential impact on the interpretation of the study results.

9.1. Statistical and Analytical Plans

No interim analysis is planned.

The study analysis will be performed following database lock upon the completion of the last patient or upon its early discontinuation whichever occurs first.

9.1.1. Protocol deviations

Protocol deviations will be reviewed and classed as major or minor during the blind-review meeting. Major protocol deviations are defined as deviations liable to bias the evaluation of the main efficacy endpoint. The following deviations will be considered as major (non-exhaustive list):

- Non compliance with the inclusion or exclusion criteria;
- Non compliance with the study treatment;
- Intake of prohibited medication;
- Noncompliance with time window.

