The sample size at a dose level will not be changed (i.e. 28 patients will need to be randomized receiving the same dose).

Dose limiting toxicity (DLT) is defined as a grade 3 or higher adverse event as defined by the "Division of AIDS table for grading the severity of adult and pediatric adverse events" (including signs/symptoms, lab toxicities and/or clinical events) considered by the Data Safety Monitoring Board as probably or definitely related to study treatment.

If more than 2 DLTs occur during the treatment period of the first four treated patients (regardless of the dose), then the enrolment of additional patients will be stopped. In addition, in case of a life threatening (grade 4) adverse reaction enrolment and treatment of ongoing patients will be immediately discontinued. In both cases, enrolment will only be resumed upon the decision of the sponsor if the Data Safety Monitoring Board can conclude that the causality of the event was unrelated or unlikely related to study treatment.

At day 29, DRV/RTV or DRV/COBI and ABX464 or its matching placebo (i.e. all treatments) will be stopped. The viral load will be monitored twice a week during the first three weeks and weekly during the next weeks. In case of Viral Rebound (VR; defined below), ART will be resumed.

Thorough pharmacokinetics analysis will be performed to characterize potential drug-drug interactions between ABX464 and DRV/RTV-COBI.

The study design is summarized below in this chart.

Clinical Study Protocol

Study code: ABX464-004

Safe sex counseling will be offered at every study visit in order to inform the patient about potential infectiousness since the viral load can rebound.

In this open-ended study, the study visits will be performed every week until Viral Rebound and then reintroduction of ARTs.

A viral load and a CD4+ count will be assessed weekly during the course of the study. However, these testings will be performed twice a week during the first three weeks following treatment interruption in order to capture as early as possible a potential early relapse.

A Viral Rebound (VR) is defined as HIV viral load > 1000 copies mL-1. If a patient meets this criterion, then ARTs should be reintroduced. The patient should be withdrawn from the study and should perform a follow-up visits every 14 days after ARTs reintroduction until the viral load has returned to undetectable levels.

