3.2. Duration of study participation

From a patient standpoint, the study participation is defined as

- Two to four weeks of screening period;
- Four weeks as combination treatment period (DRV/RTV or DRV/COBI + ABX464/placebo);
- A treatment interruption period that will last until the viral load rebounds.
- Some follow-up visits, every 14 days, after ARTs reintroduction until the viral load has returned to undetectable levels. In any case, the liver function testings should be peformed during these visits for at least 28 days after treatment interruption or premature study discontinuation.

Overall, the minimal study duration will be 49 days.

In case of no Viral Rebound then the end of study will be 3 months after treatment interruption with the possibility for the patient to be enrolled in long term-observational follow-up study.

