5.2.6. Treatment interruption period Visits (\pm 2 days)

During the treatment interruption period study visits should be performed weekly until viral load rebounds. The following examination should be performed during these visits.

- Physical examination and vital signs;
- Hematology;
- Biochemistry and urinalysis;
- Viral Load, CD4/CD8 count;
- Blood collection for HIV reservoir assessment;
- Urine pregnancy test for all women of childbearing potential;
- Adverse Events reporting.

However, during the first three weeks (after treatment interruption), the Viral Load and the CD4/CD8 count should be controlled twice a week.

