9.1.2. Definition of study analysis sets

The following datasets will be defined and used for the analyses:

- The Safety dataset (SAF population) is defined as those patients included in the study, who have received at least one dose of the study treatment.
- The Full Analysis dataset (FAS population) is defined as those patients included in the study, who have received at least one dose of the study treatment, and who have at least one baseline data.
- The **Per Protocol dataset (PP population)** is defined as those patients of the FAS population without any major protocol deviation.

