9.1.3. Patients/Subjects disposition

The number and the percentages of patients enrolled and included in each of the populations will be tabulated. The reason for patient exclusions from each of the populations will also be listed. In addition, the number of discontinued patients with their reason for discontinuation will be tabulated.

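### The time-window bullet in 9.1.1 has no visit limit, so unless blind review narrows it, per-protocol exclusion rises with Time To Viral Rebound and can shrink a real difference

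*Protocol*

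**What the plan says.** Section 9.1.1 has deviations classed as major or minor at a blind-review meeting. It gives a general test: "Major protocol deviations are defined as deviations liable to bias the evaluation of the main efficacy endpoint". It then introduces four bullets with "The following deviations will be considered as major (non-exhaustive list", and the last bullet is "Noncompliance with time window". No visit, study period or size of departure is named.

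Section 9.1.2 defines the PP set as "those patients of the FAS population without any major protocol deviation", so one major deviation is enough. Section 9.2 runs the efficacy analyses on both FAS and PP unless otherwise specified.

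On visits after treatment stop, 5.2.6 states "During the treatment interruption period study visits should be performed weekly until viral load rebounds", with a window of ±2 days in its heading and in the flow chart (5.1). Section 3.1.1 sets the sampling: "The viral load will be monitored twice a week during the first three weeks and weekly during the next weeks". Section 3.2 gives the upper limit: "In case of no Viral Rebound then the end of study will be 3 months after treatment interruption".

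Time To Viral Rebound is a secondary objective (2.2), but it is the endpoint on which the trial was sized (9.4): medians of 7 days on placebo and at least 28 days on ABX464, with 7 and 21 evaluable patients. Section 9.1.3 adds that "The reason for patient exclusions from each of the populations will also be listed".

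**The concern.** The number of post-interruption windows a patient must meet is set by that patient's own rebound time. If any missed window excludes, patients with late rebound are the most likely to leave PP. A long time to rebound is what ABX464 is meant to produce, so more of the informative patients would leave the active arm.

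Review blind to treatment does not prevent this, because the selection acts through rebound time and not through arm. Section 6.5 blinds to treatment only, and nothing in 9.1.1 hides rebound time from the meeting.

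What is at stake is a PP result that disagrees with the FAS for a reason unrelated to the drug. With 7 placebo patients such a disagreement would be hard to interpret.

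**Working it through.** **Plan's own figure.** Exponential medians of 7 and 28 days give a hazard ratio of 7/28 = 0.25. With 3:1 allocation and two-sided 0.05, the events needed for 80% power are (1.96 + 0.84)² / (0.75 × 0.25 × (ln 0.25)²) = 7.84 / 0.360 ≈ 22. A Lakatos log-rank calculation gives 78.6% at 21 days and 82.4% at 28 days of follow-up. The stated 80% is therefore reproducible, and the medians are used below as given.

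**Windows at stake.** Scheduled interruption visits are days 3.5, 7, …, 21 (six), then 28, 35, …, 91 (ten), 16 in all. Rebound at day 7 passes 2 windows, at day 28 passes 7, and no rebound by day 91 passes 16.

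**Chance of staying in PP, interruption visits only.** With an independent breach probability q per visit this is (1 − q)^k. At an assumed q = 5%:
- k = 2: 0.95² = 0.90
- k = 7: 0.95⁷ = 0.70
- k = 16: 0.95¹⁶ = 0.44

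**Direction.** If breaches occur at a constant rate d, an exponential hazard L becomes L + d among those kept. The hazard ratio becomes (L_active + d)/(L_placebo + d), which moves from 0.25 toward 1 as d grows. If the two hazards are equal it stays at 1.

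**Size.** Each rebound time is weighted by its retention, E[(1 − q)^(5+k)], counting five on-treatment visits (D7, D14, D21, D25, D28) and k interruption visits up to detection or day 91. In the clustered case q follows a beta distribution with the same mean and within-patient correlation 0.2. In the exempt cases only the weekly visits after day 21 count. The values of q and the correlation are assumptions. Differences are taken before rounding.

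| PP medians, placebo / ABX464 (difference), days | q = 1% | 2% | 5% | 10% |
|---|---|---|---|---|
| True | 7 / 28 (21) | 7 / 28 (21) | 7 / 28 (21) | 7 / 28 (21) |
| All visits, independent | 6.8 / 26.4 (19.6) | 6.6 / 24.9 (18.3) | 6.2 / 20.8 (14.6) | 5.5 / 15.4 (9.9) |
| Twice-weekly exempt, independent | 7.0 / 26.9 (19.9) | 7.0 / 25.8 (18.9) | 6.9 / 23.1 (16.2) | 6.8 / 19.7 (12.9) |
| All visits, clustered 0.2 | 6.9 / 27.6 (20.7) | 6.9 / 27.2 (20.3) | 6.7 / 26.0 (19.3) | 6.4 / 24.1 (17.7) |

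With both the exemption and clustering of 0.2, the ABX464 median at 5% is 26.1 days.

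**Shape of the rebound-time distribution.** At 5% over all visits, the ABX464 median is 16.8 days (independent) or 24.6 (clustered) for Weibull shape 0.7, and 25.8 or 27.4 for shape 2.

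**Patients kept.** Interruption visits alone, independent at 5%, leave 14.4 of 21 and 6.0 of 7. On-treatment visits add further loss, but it is equal in expectation in both arms and causes no selection on rebound.

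**Check of the remedy.** With on-treatment windows only, retention is (1 − q)⁵ = 95/90/77/59% in both arms at 1/2/5/10%, and the medians stay at 7 and 28 days. Now consider only the interval that dates rebound, at q = 10%. A rebound by day 3.5 has one visit at stake and any later one has two.
- Placebo: retained fraction 0.9 × 0.293 + 0.81 × 0.707 = 0.836. Half of it is reached where the true cumulative probability is 0.484, which is 6.7 days.
- ABX464: 0.9 × 0.083 + 0.81 × 0.917 = 0.8175. Half is reached at 0.495, which is 27.6 days (28.1 if a patient without rebound has only one visit at stake).

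**The case against.** The strongest objection is that the bullet must be read with the sentences before it. Deviations are classed at a meeting, and major means likely to distort the main efficacy endpoint. A late sample in a patient who is still suppressed at the next visit does not affect the dating of rebound, so it need not be major. This stands in part. A reader might infer that the protocol makes a missed window at any visit automatically major; it does not say that, and the meeting could apply the bullet narrowly. But the list is introduced as deviations that will count as major, and the bullet carries no limit of its own.

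A second objection is that such detail belongs in the SAP, which is not shown. That would answer a missing rule. Here the rule is stated, and stated too broadly.

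Third, the size is assumed throughout. With ±2 days around twice-weekly samples the early windows overlap, so a breach in the first three weeks is mostly a missed visit, and the all-visits row of the table is an upper case. The large-sample standard error of a 28-day exponential median with 21 patients is about (28/ln 2)/√21 ≈ 9 days, so a shift of 2 to 5 days would hardly stand out. This stands, and it is why the point is optional.

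Fourth, the primary objective is safety (2.1), the synopsis summarises efficacy descriptively, and no decision is tied to PP. This also stands.

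**Conclusion.** The point holds as a conditional one: unless the blind review narrows the bullet, PP exclusion rises with Time To Viral Rebound. If ABX464 delays rebound, the PP difference then moves toward no effect.

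Under the protocol's medians and exponential times, a 5% breach rate per visit takes the 21-day difference to between 14.6 and about 19 days, depending on clustering and on whether the twice-weekly windows count. At 1-2% the loss is at most 2.7 days (21 − 18.3). The result rests on an assumed breach rate that is equal in the two arms.

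Two stronger conclusions are tempting and not supported. One is that the rule could create a false drug effect: with equal rebound times both arms are selected alike. The other is that the trial's efficacy result as a whole is biased: the FAS keeps all these patients, the endpoint is secondary, and the listed reasons for exclusion would make the loss visible. Grade: cheap improvement, optional.

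**What to change.** Reword the fourth bullet of 9.1.1 as: *Time-window noncompliance at visits scheduled for all patients (up to and including treatment stop), where it could bias the main efficacy endpoint.*

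Add: *Visit-timing deviations after treatment stop do not by themselves exclude a patient from PP. Only a sampling gap that prevents dating of rebound is referred to blind review, judged on one interval per patient: the one in which rebound was detected, or the last one if there was no rebound.*

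Exclusion then no longer accumulates with follow-up. The cost is two or three sentences, to be settled before the blind-review meeting. The downside is that PP keeps some patients whose rebound dates are known less precisely. No visit schedule or clinical rule changes.
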